Randomized Prospective Clinical Analysis of Ultrasound-guided vs. Landmarkguided Biceps Corticosteroid Injections

PI: [name]

Co-investigators:

[name], MD, [name], MD

Introduction

Biceps tendinitis typically includes pain in the anterior shoulder that is reproduced with provocative maneuvers. Corticosteroid injections have been a mainstay of conservative management of biceps tendonitis. Many physicians have recently added ultrasound guidance to the injection to ensure accurate placement in the tendon sheath. Studies have shown that ultrasound guidance is more accurate than landmark guidance. However, the clinical significance of the accurate placement of the injection into the sheath is not clear.

Study Aim

Using randomization, prospectively determine superiority of either ultrasoundguided or landmark-guided biceps corticosteroid injections with regard to various clinical variables described at three weeks and three months.

Hypothesis

There will be a significant clinical difference in outcomes with ultrasound-guided being superior tolandmark-guided biceps corticosteroid injections at threeweeks and threemonth follow up.

Inclusion Criteria

Pain at intertubercular groove Anterior humeral pain Positive Speed's Test Bicep's tendinitis is primary diagnosis for patient Patient agrees to follow up and consent

Exclusion Criteria

Prior biceps surgery or injections Prior SLAP or labral repair Concomitant shoulder arthroplasty

Methods

Patients are diagnosed with biceps tendinitis in the outpatient clinic. After diagnosis, all the patients that meet inclusion/exclusion criteria will be offered to enroll in the study. Study will be described to the patient with regard to protocol and consent. All questions regarding the study will be answered, and it will be explicitly described that the

study involvement will not change clinical care. It will be explained that we expect a follow up appointment in three weeks and three months.

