After collection of informed consent, the patient will be randomized to either ultrasound-guided or landmark-guided injection. The patient will complete clinical scores at the initial visit prior to the injection. After injection, the patient will have follow up scheduled for three weeks and three months. To ensure patient blinding, an ultrasound will be placed on the patient for both groups, but only active imaging with be performed for the ultrasound-guided patient group. For clinician blinding, a different clinician than the injecting clinician will perform the follow up examinations. The patient is instructed to not seek additional injections during the study.

Enrollment: 40-60 patients will be enrolled

Data collection will be performed as described below:

Pre-Procedural Data:

- Clinical Assessment Information (Symptomatic and asymptomatic side)
- Clinical Questionnaires
 - o Pain VAS
 - o ASES
 - o SST
 - o SANE
 - Biceps Specific Questions
 - o Fatigue pain
 - Anterior Shoulder Pain (0-10)
 - Presence of spasms
 - Provocative Maneuvers
 - o Tenderness at the bicipital groove with arm at neutral
 - O'Brien's, Speeds, Yergason's test

Post-Procedural Evaluation (same data as pre-operative visit)

- 3weeks
- 3 months

All data will be stored on a dedicated research computer on a local hard drive that requires password access, which only study personnel will possess. All patient identifying data will be removed and only demographic information will be included with an anonymous patient ID being ascribed. Statistical analysis will be performed in a blinded manner until results are final. These will include non-parametric comparison of groups with regard to all outcomes.

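### The trial aims to show superiority, but no outcome is named as primary and it is not settled whether superiority is needed at one visit or both

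*Protocol*

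**What the plan says.** Four places in the Protocol bear on what would count as success.

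- **Study Aim:** the trial is to determine "superiority of either ultrasoundguided or landmark-guided biceps corticosteroid injections with regard to various clinical variables described at three weeks and three months". No direction is fixed and no variable is named.
- **Hypothesis:** this is narrower. It expects a significant clinical difference, with "ultrasound-guided being superior tolandmark-guided biceps corticosteroid injections at threeweeks and threemonth follow up". Direction is fixed and the visits are joined by 'and', but again no outcome is named.
- **Methods, data collection list:** four questionnaires, three biceps-specific items and four examination items before the injection, then "Post-Procedural Evaluation (same data as pre-operative visit") at three weeks and three months.
- **Methods, final paragraph:** "These will include non-parametric comparison of groups with regard to all outcomes". The preceding sentence adds "Statistical analysis will be performed in a blinded manner until results are final".

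No outcome or visit is called primary, nothing is ranked, and no success rule is given. The one design figure, "Enrollment: 40-60 patients will be enrolled", is not tied to any outcome.

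**The concern.** A superiority trial needs a stated result that decides whether superiority has been shown. Here the aim points to a set of unnamed variables and the analysis points to all of them.

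Taken at its broadest, the aim would be met by a difference on any outcome, at either visit, in either direction. Taken most strictly, the hypothesis would be met only by the same outcome favouring ultrasound at both visits. Several readings lie between these, and nothing in the document selects one.

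At stake is the chance of a false superiority claim, which differs widely between the readings. So is the handling of conflicting results: if one scale favours ultrasound and another does not, or three weeks and three months disagree, the protocol gives no way to decide what the trial has shown.

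**Working it through.** **Inputs from the Protocol**

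- Outcomes: Pain VAS, ASES, SST, SANE (4); fatigue pain, anterior shoulder pain, spasms (3); groove tenderness, O'Brien's, Speed's, Yergason's (4). 4 + 3 + 4 = 11. The general clinical assessment item is not counted, so 11 is a minimum.
- Follow-up visits: 2. Comparisons: 11 × 2 = 22.
- Enrolment: 40–60 in total. This figure cannot be reproduced, because no alpha, power, effect size or SD is given. It is used below only to set arm sizes.

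**Assumptions, not in the Protocol**

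No true difference; each comparison unadjusted at two-sided 0.05; 1:1 allocation (20 or 30 per arm); no dropout. Correlation between outcomes is ro, and between visits for the same outcome rv. Correlation between different outcomes at different visits is ro × rv.

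**Step 1: simple bound.** If the 22 tests were independent, the chance of at least one false positive would be 1 − 0.95^22 = 67.6%. The outcomes are certainly correlated, so this is an upper reference point, not an estimate.

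**Step 2: correlated normal test statistics.** 400,000 draws per setting (200,000 at ro = 0.9), threshold |z| > 1.96, rv from 0.3 to 0.7.

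| ro | (1) Any outcome, any visit, either direction | (2) Any outcome, any visit, favouring ultrasound | (3) Same outcome favouring ultrasound at both visits |
|---|---|---|---|
| 0.5 | 45.6–50.6% | 23.2–26.5% | 2.0–6.2% |
| 0.7 | 34.4–38.7% | 17.2–19.9% | 1.6–4.6% |
| 0.9 | 20.8–23.9% | 10.5–12.1% | 0.9–2.6% |

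At the extreme ro = rv = 0.9 the figures are 17.8%, 8.8% and 4.2%. For a single named comparison the reference is 5%, or 2.5% in one direction.

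**Step 3: patient-level check.** 4,000 simulated trials per setting, 20 or 30 per arm, ro 0.5 and 0.7, rv 0.3 and 0.7. Six items were treated as 0–10 scales (Mann-Whitney) and five as yes/no at 50% prevalence (Fisher exact). Results: 32–46%, 16–25% and 1.0–3.7%. These are somewhat lower, with the same ordering.

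**Step 4: one named outcome, visits tested in a fixed order.** The second visit is tested only if the first is significant, so any false claim under no difference requires the first test to be falsely significant: 5%. Both visits falsely favouring ultrasound has probability P(Z1 > 1.96 and Z2 > 1.96), which is 0.0024 at rv = 0.3 and 0.0083 at rv = 0.7, or 0.2–0.8%.

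**Step 5: power under that rule.** 20,000 simulated Mann-Whitney pairs on a 0–10 scale, assumed benefit 0.8 SD at both visits, rv 0.3 and 0.7.

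| Total patients | First test significant | Both significant |
|---|---|---|
| 40 | 66% | 47–53% |
| 60 | 84% | 72–76% |

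**The case against.** **The hypothesis already says 'and'.** Read plainly, it requires both visits, and it fixes the direction. On that reading the false-claim rate is 1.6–6.2% against a one-direction reference of 2.5%, so inflation is modest or absent. This is the strongest point, and it stands as one legitimate reading. It does not settle the matter. The aim uses the same 'and' to list assessment times and allows either technique to win. Neither sentence says that the same outcome must succeed at both visits. Even if the visit rule were accepted, the outcome would remain unnamed.

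**Blinded analysis protects against selection.** It limits choosing results by their direction. It does not say which outcome decides, and once the results are final any of the 22 could be put forward.

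**A result favouring landmark guidance cannot support this hypothesis.** True of the hypothesis, but it would meet the aim as worded. Conflict between outcomes stays open in any case.

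**The SAP may cover this.** For the test, the alpha level, the adjustment and any gating, that is fair; their absence is no finding here. The choice of deciding outcome and visit rule is a design decision, and the protocol states a superiority objective without making it.

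**The error rates rest on assumed inputs.** They do, and stronger correlation lowers the first two. The defect itself does not depend on them.

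**Conclusion.** The concern holds and should be fixed before outcome data are seen. The protocol states a superiority objective but leaves open which of at least 22 comparisons decides it, and its aim and hypothesis do not agree on direction or settle the visit rule.

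Under the stated assumptions, the chance of a false claim is 34–51% on the broadest reading of the aim, 17–27% if only differences favouring ultrasound count, and 1.6–6.2% on the strictest reading of the hypothesis. The inflation is large on the first two readings and small or nil on the third. Confidence is high that no primary outcome is named, which is plain from the text. The size of the effect is illustrative, since alpha, sidedness, correlations and allocation are all assumed.

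**What to change.** Name one primary outcome and state which visit decides, or state that both must succeed. The choice of outcome and the visit order belong to the investigators. Example wording:

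> The primary outcome is [one outcome], compared between groups by a two-sided Mann-Whitney test at 0.05, first at [visit A] and, only if significant, at [visit B] at 0.05. Superiority is concluded at each visit where the test is significant in this order; the hypothesis of superiority at both visits is met only if both are significant in favour of ultrasound. All other comparisons are secondary and do not support the superiority claim.

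Then align the Study Aim and Hypothesis with that wording. The test named suits a scale outcome. The test, level and ordering may sit in the SAP if preferred; the primary outcome and the visit rule should be in the protocol.

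**Cost.** A few sentences, with no change to data collection or sample size. Significant secondary results could no longer support the superiority claim. The rule also exposes the limited power at the lower end of enrolment: with 40 patients and an assumed 0.8 SD benefit, both tests succeed in only about half of trials. Dropout lowers this further. With an assumed 20% loss (16 per arm), and taking the Mann-Whitney test's relative efficiency as 0.955, the first test succeeds in about Φ(0.8 × √(16/2 × 0.955) − 1.96) = Φ(0.25) ≈ 60% of trials.

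### The only analysis named, a non-parametric group comparison, states no adjustment for the baseline scores already collected; rank ANCOVA stays non-parametric and is more precise when baseline and follow-up correlate

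*Protocol*

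**What the plan says.** The last paragraph of the Protocol's Methods gives the whole statistical plan in one sentence: "These will include non-parametric comparison of groups with regard to all outcomes". It names no test, covariate or change score.

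The same section provides for the baseline: "The patient will complete clinical scores at the initial visit prior to the injection". The data collection list then repeats the set at both follow-up visits: "Post-Procedural Evaluation (same data as pre-operative visit". Pain VAS, ASES, SST, SANE and the 0-10 anterior shoulder pain item therefore each have their own pre-injection value.

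The size is "Enrollment: 40-60 patients will be enrolled", with no effect size, SD, alpha, power or correlation given. The Hypothesis section expects that "There will be a significant clinical difference in outcomes with ultrasound-guided being superior".

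**The concern.** A plain non-parametric comparison can be read in two ways. A rank test on follow-up scores ignores the baseline. A rank test on change scores uses it, but with a weight fixed at one whatever the data show. Follow-up does better when the correlation is low and change when it is high, so choosing between them without knowing the correlation is a guess. Rank ANCOVA estimates the weight from the data and keeps the sponsor's non-parametric approach.

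At 20-30 per arm this matters. Only large differences are detectable, and chance imbalance at baseline is common. An unadjusted result is less likely to settle the hypothesis and depends more on how the arms happened to fall at entry.

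**Working it through.** **Inputs.** From the protocol: two randomised arms, 40-60 patients in total, the same scores before injection and at two follow-ups. Assumed because the protocol does not give them: 1:1 allocation (20-30 per arm), two-sided alpha 0.05, no dropout, a true difference of 0.7 SD, and baseline-to-follow-up correlation ρ from 0 to 0.7. The protocol has no power figure to reproduce.

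**Variance argument** (equal SDs, follow-up variance set to 1):

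- follow-up alone: 1
- change: 2(1 − ρ), that is 2 / 1.4 / 1.0 / 0.6 at ρ = 0 / 0.3 / 0.5 / 0.7
- baseline-adjusted: 1 − ρ², that is 1 / 0.91 / 0.75 / 0.51

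Since 2(1 − ρ) − (1 − ρ²) = (1 − ρ)², the adjusted variance is never above that of change, nor above 1. Change overtakes follow-up only when ρ exceeds 0.5.

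**Detectable difference at 80% power** (test on means): (1.960 + 0.842) × √(2/n) × √(1 − ρ²).

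- n = 20 per arm: 2.802 × 0.316 = 0.89 SD unadjusted; 0.85 / 0.77 / 0.63 SD adjusted at ρ = 0.3 / 0.5 / 0.7
- n = 30 per arm: 2.802 × 0.258 = 0.72 SD unadjusted; 0.69 / 0.63 / 0.52 SD adjusted

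**Simulation of the rank methods**: 20,000 runs per cell, Monte Carlo error about 0.35 points. Quade's method is a t-test on the residuals from regressing outcome ranks on baseline ranks. Power in % at ρ = 0 / 0.3 / 0.5 / 0.7:

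| Data shape, n per arm | Mann-Whitney, follow-up | Mann-Whitney, change | Quade |
|---|---|---|---|
| Normal, 20 | about 55 throughout | 32 / 42 / 56 / 77 | 55 / 59 / 66 / 80 |
| Normal, 30 | 73 / 74 / 73 / 73 | 44 / 59 / 73 / 92 | 73 / 77 / 84 / 94 |
| Rounded and clipped to 0-10, 20 | 54 throughout | 30 / 40 / 51 / 72 | 54 / 57 / 65 / 79 |
| Skewed, floored 0-10, 20 | 52 throughout | 21 / 27 / 35 / 46 | 52 / 54 / 62 / 75 |
| Skewed, floored 0-10, 30 | 70 / 71 / 70 / 70 | 29 / 39 / 49 / 64 | 70 / 74 / 80 / 90 |

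For normal data at 20 per arm, Quade's gain over the better unadjusted reading is 0 / 3 / 10 / 3 points, and over the worse one 23 / 16 / 10 / 25 (rounded table entries can differ from these by a point). A fresh set of 10,000 runs per cell gave 55-56% for follow-up, 32 / 43 / 56 / 77% for change and 56 / 58 / 65 / 80% for Quade. Type I error was 4.4-5.4% for every method.

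**Limits of the gain.** It is near zero at ρ of 0-0.1. Against change scores it has gone by ρ = 0.8 (91% each), and at 0.9 the figures are 99.6% for change and 99.1% for Quade.

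**In patients.** At ρ = 0.5, Quade with 20 per arm has 65.6% power; Mann-Whitney on follow-up has 63.2% with 24 per arm and 67.6% with 26. Interpolating, 24 + 2 × (65.6 − 63.2)/(67.6 − 63.2) ≈ 25 per arm, so about 10 patients in total.

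**Chance imbalance.** At 20 per arm the standard error of the baseline difference is √(2/20) = 0.32 SD, so the arms differ by at least that much in about 32% of trials. Within those trials, with no true effect, false positives at ρ = 0.3 / 0.5 / 0.7 are 6.4 / 8.3 / 11.8% for follow-up, 10.3 / 9.0 / 7.4% for change and 4.8 / 4.6 / 4.9% for Quade.

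**Raw-score ANCOVA** is not a safe replacement for the test. On the skewed scale at 20 per arm it has 46 / 47 / 53 / 63% power, below the unadjusted follow-up test at low ρ. Its 95% CI covers at 94-95% in all shapes.

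**The case against.** The strongest reply is that the protocol fixes only a family of methods. Its wording is not exhaustive, Quade's method is itself a non-parametric group comparison, and an SAP could name it without contradicting anything. The unadjusted test is also valid: overall error is nominal, and the raised false-positive rates apply only to the imbalanced subset of trials. All of this is true. It makes the point one of efficiency, not error. But the stated method still has a better version of the same kind, using data the protocol already plans to collect.

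The size of the gain rests on assumed inputs and on data shape. Entry requires symptoms and a positive test, which may narrow the baseline spread. With only the upper half of a normal baseline kept (20 per arm, nominal ρ 0.3 / 0.5 / 0.7, realised within-arm 0.18 / 0.32 / 0.50), power was 57 / 63 / 71% for follow-up, 51 / 63 / 81% for change and 58 / 67 / 81% for Quade. The gain over the better reading falls to about 1 / 4 / 0 points. This stands and tempers the claim, although Quade was still never more than about 1 point worse.

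Finally, Quade gives no difference in score points. If raw ANCOVA supplies one, the two can disagree: on skewed scores they differed on significance in 15-21% of simulated trials. That is a reason to say in advance which one is the test. It is not a reason to leave the baseline out.

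**Conclusion.** The point holds as an improvement the protocol should make. At assumed correlations of 0.3-0.7, rank ANCOVA beat both unadjusted readings in the normal, bounded and skewed shapes. The gain over the better reading on normal data is about 2-4 points at 0.3 and 0.7 and about 10 at 0.5. With a narrowed baseline it is only 0-4. In no setting tried did it cost more than about 1 point. Its main merit is that the sponsor need not guess the correlation, where a wrong choice between follow-up and change costs 16-25 points at 0.3 or 0.7.

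These figures assume 1:1 allocation, two-sided 0.05, no dropout and one outcome with a 0.7 SD effect. With 0.5 SD the gain over the better reading is 0 / 2 / 7 / 2 points at ρ = 0 / 0.3 / 0.5 / 0.7, and with 0.9 SD it is −1 / 2 / 9 / 1. Confidence is medium because the correlation is unknown.

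**What to change.** For Pain VAS, ASES, SST, SANE and anterior shoulder pain, state that the groups are compared at each follow-up visit by rank ANCOVA (Quade), with that outcome's own pre-injection value as covariate. Report a between-group difference in score points with its 95% CI. A raw-score ANCOVA may supply this as a supporting estimate; say in advance that the rank analysis remains the test.

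Fatigue pain, whose scale is not given, belongs here only if it is scored. The yes/no items (spasms, groove tenderness, O'Brien's, Yergason's) are outside this change. Speed's test needs no baseline adjustment, since "Positive Speed's Test" is an inclusion criterion and every patient has the same value at entry.

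The cost is a short addition to the analysis wording, with no new data, visits or patients.
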